1.2 Controls and Minimization of Bias

Due to the inherent difference in utility of standard and PAC modes, study subjects and study staff will not be blinded to the compression mode. However, the following bias control methods will be employed in this study:

- Selection bias will be limited by consecutively enrolling eligible subjects.
- Spectrum bias will be limited by using a population expected to represent the general population at the investigational site, without regard to race or ethnicity.
- PAC will be randomly assigned to either the first or second breast imaged to mitigate subject-learning bias associated with the amount of compression required for image acquisition.
- Reading order bias will be limited by randomizing the order of image set presentation to the readers.
- Readers conducting image quality evaluations will be blinded to the compression mode used to obtain the images.
- A minimum of three (3) radiology technologists will conduct the study procedures to mitigate bias introduced by technologist-specific practices.

2. DEVICE/PRODUCT DESCRIPTION

2.1 Identity, Mechanism, and Function of Investigational Device

Name: Patient-assisted Compression (PAC), Senographe Pristina 3D

Modality/Type: Imaging, Women's Health

Manufacturer: GE

Software version: Senographe Pristina 1.0, Axis version 1.50

Regulatory Status: Post-market device (PAC) used off-label in this pre-market research study

Note: A record of number of products issued, along with applicable identification numbers (e.g. serial/lot/batch) and components/accessories used in this study will be retained by the Sponsor as part of the clinical history file (CHF), as required by applicable laws and regulations.

Senographe Pristina is a commercial mammography medical device consisting of the Senographe Pristina FFDM system (2D) and Senographe Pristina 3D (DBT option). The platform is an evolution of the cleared/approved Senographe Essential FFDM system (2D) and SenoClaire DBT option (3D). Senographe Pristina includes the same clinical applications as traditional mammography systems and is designed to improve workflow while maintaining imaging capabilities and image quality of FFDM and DBT breast imaging. The DBT option will be the focus of this study, as PAC is FDA-cleared for use with the Senographe Pristina FFDM system.

Senographe Pristina includes the hardware and software components required for multi-modality functioning and is designed to improve patient experience, patient throughput, and radiographer experience. The system offers two compression modes – standard mode and the optional PAC mode

personally refine breast compression using a hand-held . PAC enables the patient to remote control (Figure 1

) after the compression has been initiated by the operator, which is required to ensure proper breast positioning.

Figure 1 –Senographe Pristina mammography device with remote control for PAC.

The research device (i.e. Senographe Pristina 3D with PAC), instructions for use, or packaging shall indicate that the research device is for use in a research investigation, in accordance with applicable regulations in the U.S., including U.S. FDA 21 CFR and other applicable laws and regulations. Senographe Pristina 3D with PAC will be exclusively used for research purposes.

The results of this study are intended to support regulatory submissions for PAC use with Senographe Pristina 3D. Results may be used to help commercialize the product in other global regions in the future, at the discretion of the Sponsor.

2.2 Mammography Review Workstation

An FDA-cleared mammography review workstation or other image review system will be used in this study to display images during reader evaluations of the image sets. Review workstations/systems are not a component of Senographe Pristina or PAC.

The study-specific images will be labelled for research use only, and the investigational image sets will be exclusively used for research purposes.

2.3 Intended Use

Senographe Pristina 3D is indicated for acquisition of multiple projection views to produce 3D digital mammography images suitable for use in screening and diagnosis of breast cancer; however, screening mammography is the focus of this study. Study procedures are intended for research purposes and are not intended as a substitute for required medical care.

2.4 Comparator

The comparator is the technologist-controlled compression mode of Senographe Pristina 3D (referred to as “TC compression” hereafter). This is considered the “standard” compression mode, which is currently approved for use with Senographe Pristina 3D.

2.5 Concomitant/Ancillary Administrations

2.5.1 Medications and Biologic Products

No medications or biologic products will be administered as part of study procedures.

2.5.2 Laboratory Tests and Sample Processing

No laboratory tests or sample processing is planned as part of the study procedures.

2.6 Accountability

Accurate and adequate records will be maintained for all devices/products, from time of shipment to the site until return or disposal of all devices issued by the Sponsor as part of this study, as required by applicable laws and regulations. The Principal Investigator (PI) will be ultimately responsible for the security and integrity of research devices/products at the investigational site during the study.

2.6.1 Issuance

The PAC product will be provided by the Sponsor. Site will be encouraged to use equipment owned by the site, such as the Senographe Pristina and image review workstations, if available. If the site does not own the required equipment, the Sponsor may provide devices for study use.

2.6.2 Disposition

Product(s) provided to the site by the Sponsor will be returned to the Sponsor, in accordance with applicable laws and regulations.

2.7 Anticipated Risks and Benefits

The device under study has undergone risk assessment, in accordance with International Standards Organization (ISO) 14971:2012. Risks have been mitigated to levels as low as reasonably possible (ALARP) and are not expected to exceed risks associated with the routine clinical breast cancer screening procedures that the subject has been prescribed outside of the study. The operator’s manual highlights warnings, cautions, and potential conventional risks associated with the exam.

Breast imaging procedures will be conducted using post-market Senographe Pristina systems with post-market PAC installed. Breast imaging procedures will be conducted per the site’s standard of care, with the exception of the

investigational imaging, which will consist of unilateral two-view (craniocaudal [CC] and mediolateral oblique [MLO]) acquisitions using PAC during DBT imaging. There will be no repeat imaging administered using PAC.

No additional medications will be administered beyond those regularly required for the subject's medical care outside of this study, and regular medication should not be adversely impacted or delayed by study participation. Post-trial care and follow-up are not required by this study.

There is no expected benefit to study subjects participating in this research. The results of this study may benefit future patients by increasing knowledge about PAC with Senographe Pristina 3D.

2.7.1 Risk Category and Rationale

The Senographe Pristina 3D system with PAC, as used in this study, is not considered a significant risk device per the 21 CFR §812.3 definition:

- 1) it is not intended as an implant;
- 2) is not purported or represented to be for a use in supporting or sustaining human life;
- 3) is not for a use of substantial importance in diagnosing, curing, mitigating, or treating disease, or otherwise preventing impairment of human health; and
- 4) it does not otherwise present a potential for serious risk to the health, safety, or welfare of a subject.

This designation of non-significant risk is supported by the study design, in which the data obtained will not be used as the sole measure of diagnosis without distinct confirmation from conventional methods, such as mammography on an approved/cleared device or other standard of care procedures at the investigational site.

3. STUDY OBJECTIVES AND ENDPOINTS

3.1 Purpose of the Study

The purpose of this study is to collect clinical evidence associated with image quality and workflow to support regulatory submissions for PAC use with Senographe Pristina 3D.

3.1.1 Primary Objective

The primary objective is to compare the acceptability of overall image quality in unilateral two-view (CC and MLO) breast images acquired using PAC and TC compression modes.

3.1.2 Secondary Objectives

The secondary objectives are:

- To evaluate the need for repeat image acquisition when using PAC and TC compression modes; and
- To evaluate acceptability of mammographic attributes for unilateral two-view breast images acquired using PAC and TC compression modes, per the *Guidance for Industry and FDA Staff - Class II Special Controls Guidance Document: Full-Field Digital Mammography System* (2012; hereafter referred to as the “Guidance”).

3.1.3 Exploratory Objectives

The exploratory objectives are:

- To collect workflow data for PAC and TC compression, and
- To collect breast thickness, radiation dose, and compression force for images acquired using PAC and TC compression.

3.1.4 Safety Objective

The objective is to collect safety information, including adverse events (AEs), serious adverse events (SAEs), and product issues.

3.2 Study Endpoints

3.2.1 Primary Endpoint

The primary endpoint is the overall image quality acceptability on a per subject-basis using a binary response of either acceptable or unacceptable for unilateral, two-view PAC and TC compression image sets.

3.2.2 Secondary Endpoints

The secondary endpoints are:

- Number of incidences per image set when the technologist and/or readers indicate a repeat acquisition for PAC and TC compression; and
- Acceptability of mammographic attributes, as defined in the *Guidance* and as described in Section 6.2 Image Attribute Review Data.

3.2.3 Exploratory Endpoints

The exploratory endpoints will be collected per subject for each study-specific 3D PAC and TC compression. The endpoints are:

- Type and incidence of technologist interventions (e.g. technologist uses footswitch to increase compression); and
- Breast thickness, radiation dose, and compression force.

3.2.4 Safety Endpoints

The safety endpoints are the type and number of AEs, SAEs, and device issues.

3.3 Summary of Study Design

This is a pre-market, clinical, single-blind, prospective, randomized research study conducted at one (1) site in the U.S.

4. STUDY DESIGN

4.1 Study Population

The study population will consist of asymptomatic adult women presenting for screening breast imaging, which is representative of the general population expected to use Senographe Pristina 3D in clinical practice.

4.2 Number Subjects

Up to 36 subjects will be enrolled into this study at one (1) site to achieve the targeted number of 30 complete and evaluable subjects.

4.3 Protection of Vulnerable Subjects

Vulnerable subjects are individuals whose willingness to volunteer in a clinical investigation could be unduly influenced by the expectation, whether justified or not, of benefits associated with participation or of retaliatory response from senior members of a hierarchy in case of refusal to participate.

The Sponsor shall avoid improper influence on, or inducement of, the subject, monitor, any investigator(s), or other parties participating in, or contributing to, the clinical investigation.

All investigators shall avoid improper influence on, or inducement of, the subject, Sponsor, monitor, other investigator(s), or other parties participating in, or contributing to, the clinical investigation.

This study does not examine any groups of subjects who are considered to be vulnerable subjects in the country in which the study is being conducted.

4.4 Eligibility Criteria

4.4.1 Inclusion Criteria

Subjects who meet all the following inclusion criteria may be included:

- 1) Are women aged 40 years or older;
- 2) Are asymptomatic and scheduled for screening mammography;
- 3) Have left and right breasts;
- 4) Have breast sizes compatible with the dimensions of a 24 x 31 cm image detector, without anatomical cut-off;
- 5) Are documented as non-pregnant based on the investigator's medical judgment and in consideration of local clinical practice standards for evidence of non-pregnancy;
- 6) Are able and willing to comply with study procedures; and
- 7) Are able and willing to provide written informed consent to participate.

4.4.2 Exclusion Criteria

Subjects who meet any the following exclusion criteria will be excluded:

- 1) Have been previously included in this study or are participating in another study expected to interfere with study procedures or outcomes;
- 2) Participated in the GE Healthcare study that investigated PAC with the Senographe Pristina FFDM system (*Study Number: 124.03-2017-GES-0002; Study Title: Patient-Assisted Compression – Impact on Image Quality and Workflow*);
- 3) Have undergone diagnostic or surgical intervention(s) or procedure(s) on either breast, including breast biopsy, lumpectomy, or reconstruction, within five (5) years (≤ 5 years) of the study exam date;
- 4) Are currently undergoing radiotherapy or chemotherapy, or have a history of prior radiotherapy treatment on either breast;
- 5) Are currently lactating; or
- 6) Have breast implants.

4.5 Recruiting and Screening

Subjects will be recruited for potential enrollment into this study from an adult asymptomatic female population scheduled for screening at the site. Subjects will be screened for enrollment against the inclusion and exclusion criteria,

and enrollment determinations will be made by the PI. Recruitment, screening, and enrollment will be conducted per the standard procedures of the investigational site. All subject participation will be voluntary.

Following recruitment, a subject will be considered enrolled (the point of enrollment) once she signs and dates the informed consent form (ICF). Once enrolled, the subject will be assigned a unique subject number, which will not contain information that could identify her (e.g. subject name or date of birth). The unique subject number will be used to label case report form (CRF) data for the subject throughout her participation in the study.

4.6 Breast of Interest Randomization

One (1) breast per subject will undergo study-specific procedures (hereafter referred to as “breast of interest”) while the second breast will be imaged per standard of care. The breast of interest will be randomized across all subjects so that approximately half the subjects will be assigned to the first imaged breast and the other half will be assigned to the second imaged breast (Figure 2).

Site technologists conducting the study will perform each subject’s mammography exam per standard practice. Thus, the laterality of the breast of interest will solely depend on which breast (left or right) the technologist images first and second in standard practice.

[figure not shown]

Figure 2 – Schematic showing image acquisitions based on the randomly-assigned breast of interest (i.e. first or second breast).

4.7 Criteria for Withdrawal/Discontinuation

A subject may withdraw from study participation at any time, for any reason, and the investigator may withdraw a subject at any time, for any reason. The reasons for withdrawal and discontinuation for any subject shall be recorded on a case report form (CRF) and reported to the Sponsor. The Ethics Committee (EC) should be notified per their notification-of-subject-withdrawal policy.

A subject shall be withdrawn from the study if a study-related PAC in either CC or MLO view is not completed (i.e. no image is acquired due to inadequate compression or positioning). If a subject withdraws or is withdrawn, all efforts will be made to complete and report study data up to the time of withdrawal. A complete final evaluation at the time of the subject’s withdrawal shall be made and recorded on a CRF. If the reason for withdrawal is related to an adverse event (AE) or serious adverse event (SAE), monitoring of the subject will continue until the outcome is evident.

Any data collected for the subject, up until the time of withdrawal or discontinuation, may still be included in the study results and provided to the Sponsor, unless the subject requests that their data not be used. The site shall document all requests by subjects regarding their data use.

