Procedures/Methods:	
The study population will consist of adult asymptomatic women presenting for screening 2D mammography. One breast of each subject will be identified as the “breast of interest,” which will undergo study-specific 3D imaging consisting of two-view (craniocaudal and mediolateral oblique) PA compression and image acquisition, followed by two-view technologist-controlled (TC) compression and image acquisition. The breast of interest will be randomly assigned to either the first breast imaged during the exam or the second breast imaged. TC compression and imaging, and procedures performed on the subject’s other breast will be conducted per standard of care.
 
Following image acquisition, 3D image quality evaluation will be conducted by MQSA-qualified readers. Prior to the reading session, images will be de-identified and the following information will be removed from the DICOM header to blind readers to the compression mode used during acquisition: time stamp, compression force, and breast thickness. The image sets will also be randomized for presentation during the image attribute reviews. Two (2) readers will evaluate each PAC and TC compression image set collected from each subject’s breast of interest and assess the acceptability of image attributes, as defined in the Guidance for Industry and FDA Staff - Class II Special Controls Guidance Document: Full-Field Digital Mammography System (2012). A third reader will provide adjudication, if there is disagreement for a given image set’s overall clinical image quality.
 
Workflow data, including the incidence of technologist intervention during acquisition and need for repeat image acquisition, will also be collected.
 
The proportion of PAC image sets that are of equal or higher acceptability than TC image sets will be calculated. A 95% confidence interval will be calculated using asymptotic method with continuity correction. The proportion of image sets indicated for repeated

	
image acquisition when using PA mode or TC mode will be summarized. Other endpoint data will be summarized using descriptive statistics. No statistical hypothesis is being tested in this study.

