5.3 Description of Study Procedures

5.3.1 Image acquisitions

Each subject will undergo her regularly scheduled breast imaging exam per standard practices at the investigational site, with the exception of the study-specific image acquisitions using PAC. The site uses combo mode (2D and 3D imaging) for screening mammography, and does not decompress between 3D and 2D imaging for a given view. Additionally, 3D acquisitions are conducted first per standard of practice. Thus, the sequence of imaging procedures will be conducted for the breast of interest, as shown in Figure 4. There shall be no repeat imaging administered using PAC mode, and standard of care will be used for imaging of the subject's other breast.

[figure not shown]

Figure 4 – Sequence of imaging procedures for the breast of interest (dark boxes = PAC, study-specific imaging, white boxes = standard of care (SoC) at the site).

A minimum of three (3) site technologists will perform the image acquisitions and related study procedures. Study procedures shall not impact the order in which the left and right breasts are imaged during the subjects' exams.

There will be two (2) study-specific image sets of the breast of interest for each subject. Image sets will consist of CC and MLO views obtained using PAC and CC and MLO views obtained using TC compression.

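### The PAC proportions cover completed PAC image sets only; Section 10 commits to no count or per-attempt analysis of women withdrawn because a PAC view yielded no image

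*Combined protocol and SAP*

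**What the plan says.** The relevant provisions of the combined protocol and SAP are spread over several sections.

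- **Withdrawal (4.7).** "A subject shall be withdrawn from the study if a study-related PAC in either CC or MLO view is not completed". The section explains this as "no image is acquired due to inadequate compression or positioning". The reason for withdrawal goes on a CRF, a final evaluation is recorded, and efforts are to be made to report data up to that time. Such data "may still be included in the study results".
- **No second attempt (5.3.1, also 2.7).** "There shall be no repeat imaging administered using PAC mode".
- **Unit of analysis (5.3.1).** "Image sets will consist of CC and MLO views obtained using PAC and CC and MLO views obtained using TC compression".
- **Order (Synopsis, Procedures/Methods).** Two-view PAC is "followed by two-view technologist-controlled (TC) compression and image acquisition".
- **Enrolment (4.2).** Up to 36 women are enrolled "to achieve the targeted number of 30 complete and evaluable subjects".
- **Objective (3.1.1).** It concerns the overall quality of "breast images acquired using PAC and TC compression modes".
- **Analysis (10.3.2, 10.4).** There are two primary summaries: the proportion of PAC sets rated at least as acceptable as the TC set, and the acceptable proportion for each mode. Both are computed over image sets, from collected data, without imputation. The first is repeated by randomised breast order.

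**The concern.** Inadequate compression is a failure of the function under study, not incidental dropout. A woman in whom PAC gives no image leaves the study, cannot have PAC repeated, and can be replaced within the enrolment cap. She contributes no complete PAC set, so she is absent from the denominators in 10.3.2. The PAC results are then conditional on PAC having worked.

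Section 3.1 says the evidence is meant to support regulatory submissions for PAC with the 3D system. No hypothesis is tested (10.1), so the estimate and its interval are the whole result and the denominator carries the meaning. A reader who sees only the planned summaries cannot tell whether no PAC attempt failed or several did. The subgroups by breast order have the same limitation.

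**Working it through.** **Inputs from the documents:** 30 evaluable subjects and a cap of 36 (4.2); a 95% asymptotic interval with continuity correction (10.3.2); a width of no more than 13% at a proportion of 95% (10.2).

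**Assumed:** the number of PAC failures f, taken from 0 to 6 because no rate is given. Six is the ceiling only if 30 completers are reached. Enrolment counts from consent (4.5), so the six spare places also cover unrelated withdrawals.

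**The plan's own precision figure, for scale.** Half-width = 1.96 × √(0.95 × 0.05 / 30) = 7.8 points. This gives 87.2% to 100% after truncation, a width of 12.8%, which reproduces the stated 13%. It omits the continuity correction; adding 1/(2 × 30) gives 85.5% to 100%, a width of 14.5%. That mismatch is a separate matter and does not affect this point.

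**Direction.** With x acceptable sets among 30 completers, the plan reports x/30. Per attempt, with non-completion counted as not acceptable, the figure is x/(30 + f). The first exceeds the second whenever x > 0 and f > 0. This holds for PAC acceptability whatever the TC rating.

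**Size, if all 30 completed PAC sets are acceptable** (the plan reports 30/30 = 100% in every row):

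| f | PAC acceptable per attempt (exact 95% CI) | Non-completion (exact 95% CI) |
|---|---|---|
| 0 | 30/30 = 100% (88.4 to 100) | 0/30 = 0% (0 to 11.6) |
| 1 | 30/31 = 96.8% (83.3 to 99.9) | 1/31 = 3.2% (0.1 to 16.7) |
| 3 | 30/33 = 90.9% (75.7 to 98.1) | 3/33 = 9.1% (1.9 to 24.3) |
| 6 | 30/36 = 83.3% (67.2 to 93.6) | 6/36 = 16.7% (6.4 to 32.8) |

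If 29 of 30 are acceptable, the plan reports 96.7%. Per attempt this becomes 29/31 = 93.5%, 29/33 = 87.9% and 29/36 = 80.6% with 1, 3 and 6 failures.

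**Paired proportion.** A failed woman's pair scores as lower if her TC set is acceptable and as equal if it is not. With three failures and 30/30 among completers, the result runs from 30/33 = 90.9% (TC acceptable in all three) through 31/33 = 93.9% and 32/33 = 97.0% to 33/33 = 100% (TC unacceptable in all three). TC follows PAC in the synopsis, so TC may not exist or may not be read after withdrawal. Figure 4, which gives the exact sequence, is not available to check this. Only the bounds are then known.

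**Subgroup.** With about 15 completers in one breast-order group (assumed), one failure turns 100% into 15/16 = 93.8%.

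**Interval for the count.** With no failures, the planned continuity-corrected interval for non-completion would be 0 to 1/60 = 1.7%. The exact upper limit is 1 − 0.025^(1/30) = 11.6%. The count therefore needs the exact method.

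**The case against.** The strongest reply is that the plan answers the question it asks. The objective and endpoint concern the quality of acquired image sets, there is no success threshold for a per-attempt figure to cross, and the protocol never claims to estimate per-attempt performance. This stands, and it is why the completed-set proportion should remain primary.

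A reader might infer that failed attempts go unrecorded or that nothing allows them to be reported. The documents do not support that. Section 4.7 puts the reason on a CRF and asks that data up to withdrawal be reported, and the general descriptive methods in 10.3.1 would permit a count. What is missing is a commitment: inclusion is permissive in 4.7, and Section 10 names no such line.

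A reader might also apply the PAC-only figures to the paired proportion. That would require TC to be acceptable in every failed woman, which the imaging order makes uncertain.

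Nor do the documents support scoring every non-completion as a repeat indication under 10.3.3. In 3.2.2, 6.1 and 6.2 that endpoint is a technologist or reader judgement.

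Failures may also be rare. The operator initiates compression (2.1) and the technologist can intervene during PAC (6.1). Some positioning failures may not be due to PAC at all. These points limit the likely size but do not show that failures will be zero.

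**Conclusion.** The point holds as a gap in the planned analysis that should be closed; it does not make the primary analysis invalid. As written, the rules remove device-related failures from the denominator of the PAC results. PAC acceptability would overstate the per-attempt result by about 3 points for one failure, 9 for three and 16 to 17 for six, when 29 or 30 of 30 completed sets are acceptable. With no failures the overstatement is zero. The paired proportion could be overstated by the same amounts or not at all, depending on TC ratings that may not exist.

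These sizes rest on 30 completers, an assumed number of failures, and counting each non-completion against PAC. They show what could happen and do not estimate what will. Uneven failure between the breast-order groups is possible, because the order was randomised to limit subject learning (1.2), but nothing in the documents shows it.

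**What to change.** Leave 4.7 and the imaging rules unchanged, and keep the completed-set proportion as the primary result. Add to 10.3.2 and 10.4:

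1. The number and proportion of subjects with a PAC view attempted but not completed, with an exact 95% CI, by recorded reason and by randomised breast order, reported beside the primary result.
2. A prespecified sensitivity analysis of PAC acceptability in all subjects with a PAC attempt, counting non-completion as not acceptable. Show the paired proportion as best-case and worst-case bounds where TC is unrated. Withdrawals unrelated to PAC stay excluded.

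Leave the repeat-acquisition endpoint in 10.3.3 as it is, and report non-completions next to it as a separate line.

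The cost is a few sentences, one results line and one small table, with no extra subjects or exposures. Using bounds avoids planning new reads of withdrawn women's TC sets. One CRF field may be needed to separate compression from positioning, since 4.7 names them together. The downsides are slightly more analysis, a possibly less favourable PAC figure, and some positioning failures charged to PAC in the sensitivity analysis. The split by reason would make those visible.
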